8.6.2 Serious adverse events

An SAE is defined as any adverse event [appearance of (or worsening of any pre-existing)] undesirable sign(s), symptom(s), or medical conditions(s) which meets any one of the following criteria:

- fatal
- life-threatening

Life-threatening in the context of a SAE refers to a reaction in which the participant was at risk of death at the time of the reaction; it does not refer to a reaction that hypothetically might have caused death if it were more severe (please refer to the ICH-E2D Guidelines).

- results in persistent or significant disability/incapacity
- constitutes a congenital anomaly/birth defect, fetal death or a congenital abnormality or birth defect
- requires inpatient hospitalization or prolongation of existing hospitalization, unless hospitalization is for:
 - routine treatment or monitoring of the studied indication, not associated with any deterioration in condition
 - elective or pre-planned treatment for a pre-existing condition that is unrelated to the indication under study and has not worsened since signing the informed consent
 - social reasons and respite care in the absence of any deterioration in the participant's general condition
 - treatment on an emergency outpatient basis for an event not fulfilling any of the definitions of a SAE given above and not resulting in hospital admission
- is medically significant, e.g. defined as an event that jeopardizes the participant or may require medical or surgical intervention to prevent one of the outcomes listed above

Medical and scientific judgment should be exercised in deciding whether other situations should be considered serious reactions, such as important medical events that might not be immediately life-threatening or result in death or hospitalization but might jeopardize the participant or might require intervention to prevent one of the other outcomes listed above. Such events should be considered as "medically significant." Examples of such events are intensive treatment in an emergency room or at home for allergic bronchospasm, blood dyscrasias, or convulsions that do not result in hospitalization or development of dependency or abuse (please refer to the ICH-E2D Guidelines).

All new malignant neoplasms will be assessed as serious under "medically significant" if other seriousness criteria are not met.

All reports of intentional misuse and abuse of the product are also considered serious adverse events irrespective of whether a clinical event has occurred.

8.6.3 SAE reporting

To ensure participant safety, every SAE, regardless of causality, occurring after the participant has provided informed consent and until 30 days following the last administration of study treatment must be reported to Novartis safety immediately, without undue delay, but under no circumstances later than within 24 hours of obtaining knowledge of the events (Note: If more stringent, local regulations regarding reporting timelines prevail). Detailed instructions regarding the submission process and requirements are to be found in the Investigator folder provided to each site. Information about all SAEs is collected and recorded on the Serious Adverse Event Report Form; all applicable sections of the form must be completed in order to provide a clinically thorough report.

1. SAEs occurring after the participant has provided informed consent until the time the participant is deemed a Screen Failure must be reported to Novartis.
2. Randomized OR Treated Participants: SAEs collected between time participant signs ICF until 30 days after the participant has discontinued from study treatment.

All follow-up information for the SAE including information on complications, progression of the initial SAE and recurrent episodes must be reported as follow-up to the original episode immediately, without undue delay, but under no circumstances later than within 24 hours of the Investigator receiving the follow-up information (Note: If more stringent, local regulations regarding reporting timelines prevail). An SAE occurring at a different time interval or otherwise considered completely unrelated to a previously reported one must be reported separately as a new event.

If the SAE is not previously documented in the Investigator's Brochure or Package Insert (new occurrence) and is thought to be related to the study treatment, a CMO & PS Department associate may urgently require further information from the Investigator for health authority reporting. Novartis may need to issue an Investigator Notification (IN) to inform all Investigators involved in any study with the same study treatment that this SAE has been reported.

Suspected Unexpected Serious Adverse Reactions (SUSARs) will be collected and reported to the competent authorities and relevant ethics committees in accordance with EU Guidance 2011/C 172/01 or as per national regulatory requirements in participating countries.

Any SAEs experienced after the 30-day period should only be reported to Novartis Safety if the Investigator suspects a causal relationship to study treatment, unless otherwise specified by local law/regulations.

8.6.4 **Pregnancy**

Pregnancies

If a female trial participant becomes pregnant, the study treatment should be stopped, and the pregnancy consent form should be presented to the trial participant. The participant must be given adequate time to read, review and sign the pregnancy consent form. This consent form is necessary to allow the Investigator to collect and report information regarding the pregnancy. To ensure participant safety, each pregnancy occurring after signing the informed consent must be reported to Novartis within 24 hours of learning of its occurrence. The pregnancy should be followed up to determine outcome, including spontaneous or voluntary termination, details of the birth, and the presence or absence of any birth defects, congenital abnormalities, or maternal and/or newborn complications.

Pregnancy should be recorded and reported by the Investigator to the Novartis Chief Medical Office and Patient Safety (CMO&PS). Pregnancy follow-up should be recorded on the same form and should include an assessment of the possible relationship to the investigational treatment any pregnancy outcome. Any SAE experienced during pregnancy must be reported.

If a female partner of a male trial participant who took study treatment in this study becomes pregnant, pregnancy outcomes should be collected. Consent to report information regarding these pregnancy outcomes should be obtained from the mother.

After consent is provided, the pregnancy reporting will occur up to one year after the estimated date of delivery.

8.6.5 **Disease-related events and/or disease-related outcomes not qualifying as AEs or SAEs**

[figure not shown]
Not applicable

8.7 **Pharmacokinetics**

Pharmacokinetic parameters are not evaluated in this extension study.

8.8 **CCI**

CCI

CCI

CCI

CCI

[figure not shown]
CCI

CCI

8.8.1 CCI

CCI

8.9 Immunogenicity assessments

Immunogenicity is not evaluated in this study.

8.10 Health economics OR Medical resource utilization and health economics

Health economics and medical resource utilization and health economics parameters are not evaluated in this study.

9 Statistical considerations

9.1 Analysis sets

For all analysis sets, participants will be analyzed according to the study treatment(s) received. The safety analysis set will include all participants that received any study treatment.

The PD analysis set will include all participants who received study treatment and had no protocol deviations with relevant impact on PD data.

9.2 Statistical analyses

9.2.1 General considerations

The safety analysis set will be used in the analysis of all safety variables.

9.2.2 Participant demographics and other baseline characteristics

Demographic and baseline characteristics of all patients in the extension study will be summarized for the safety population.

9.2.3 Treatments

The safety set will be used for the analyses below. Categorical data will be summarized as frequencies and percentages. For continuous data, mean, standard deviation, median, 25th and 75th percentiles, minimum, and maximum will be presented. The duration of exposure (in weeks) will be summarized by means of descriptive statistics using the safety set.

Concomitant medications and significant non-drug therapies prior to and after the start of the study treatment will be listed according to the Anatomical Therapeutic Chemical (ATC) classification system.

9.3 Primary endpoint(s)/estimand(s) analysis

The primary aim of the study is to assess the long-term safety of LTP001 in participants with PAH. Safety assessment will include AEs, SAEs, vital signs, ECGs, and safety laboratory measurements.

9.3.1 Definition of primary endpoint(s)

Adverse events (AEs)

Study emergent AEs in the extension study will be summarized and listed. Also, all study emergent AEs in both the parent study and extension study will be summarized.

Consistent with the parent study CLTP001A12201 definitions, AEs starting after the first dose of study medication or events present prior to start of treatment but increased in severity based on preferred term will be classified as a treatment emergent AE. The following treatment emergent adverse events summaries will be produced:

- by primary system organ class and preferred term
- by primary system organ class, preferred term and maximum severity
- by Standardized MedDRA Query (SMQ) and preferred term.

The number and percentage of participants with adverse events will be summarized.

Vital signs

Vital signs data will be summarized by visit/time.

Electrocardiogram (ECG)

All ECG data, including PR, QRS, QT, QTcF and RR, will be listed by participant and visit/time, and abnormalities will be flagged. Summary statistics will be provided by visit/time. Categorical Analysis of QTcF (Fridericia's formula) interval data based on the number of participants meeting or exceeding predefined limits in terms of absolute QT or QTc intervals or changes from baseline will be presented. The number and percentage of participants with clinical notable QTcF will be summarized.

Laboratory data

All laboratory data will be listed by participant and visit/time, and abnormalities will be flagged if normal ranges are available. Summary statistics will be provided for each lab parameter at each visit.

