- The treatment duration will be up to 52 weeks.

- The visit frequency will include visits at weeks 1, 5, 13, 26, 39, 52, and 56.

Treatment of interest

The treatment of interest is LTP001 [REDACTED] mg daily on top of allowed standard of care treatment for PAH. The dose of the allowed concomitant medication should remain stable during the trial.

Number of Participants:

The study population is comprised of male and female adults with PAH. A total of approximately 40 participants are planned to complete the parent study CLTP001A12201 and meet the study entry criteria for this open label extension study.

Key Inclusion criteria:

- Written informed consent must be obtained before any assessment is performed.
- Participant is currently completing the Novartis-sponsored study CLTP001A12201 in PAH and completed key efficacy and safety procedures up to the end of treatment of the parent study, without meeting discontinuation criteria in the parent study.
- Willingness and ability to comply with scheduled visits, treatment plans and any other study procedures.
- In the opinion of the Investigator the participant would benefit from LTP001 treatment.

Key Exclusion criteria:

- History of hypersensitivity to the study treatment.
- Required or planned transplant or heart/lung surgery.
- Acute or chronic impairment (other than dyspnea), which would limit the ability to comply with study requirements, including interference with physical activity or execution of study procedures such as 6MWT (e.g., angina pectoris, claudication, musculoskeletal disorder, need for walking aids).
- Permanent discontinuation of Novartis drug in the parent study due to toxicity or disease progression, non-compliance to study procedures, withdrawal of consent or any other reason.

Treatment Groups:

Active treatment: LTP001 administered as [REDACTED] mg once daily CCI [REDACTED] (CCI [REDACTED]). Investigational study treatment dose adjustments and/or interruptions are not permitted.

Data Monitoring/Other Committee:

Yes; the DMC instituted for the parent study will also receive data from this extension study (see [Section 10.1.4 Committees Structure](#)).

Key words:

Pulmonary arterial hypertension, pulmonary vascular resistance, 6 minute walk distance, time to clinical worsening, SMURF1 inhibitor, echocardiography, patient reported outcomes

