2.3 Benefit/Risk assessment

Potential risks are based on the mechanism of action, the nonclinical toxicology data, and the safety data from the FIH study.

LTP001 is the first SMURF1 inhibitor to be developed. Based on current understanding of SMURF1 biology, there are no concerns directly related to this mechanism of action; and, because LTP001 is first-in-class, there are no previously identified clinical safety risks (i.e., no known class effects).

Preclinical data

CCI

CCI

Clinical data

Single doses of LTP001 CCI mg, CCI mg, CCI mg, CCI mg, CCI mg and CCI mg were well tolerated and did not show safety signals for LTP001 in the first in human study.

Multiple doses of LTP001 CCI mg, CCI mg, CCI mg, CCI mg and CCI mg once daily and CCI mg bid were well tolerated. CCI

CCI , clinical laboratory assessments, ECGs, and vital signs did not show significant abnormalities. CCI

The risk to participants in this trial will be minimized by adherence to the eligibility criteria, close clinical monitoring, regular safety data reviews, and pre-specified rules for automatically stopping the study should unanticipated safety issues suddenly arise.

No reproductive toxicology studies have been performed for LTP001. Women of child-bearing potential will be only enrolled if they use highly effective contraception methods.

Additional details about potential risks of LTP001 can be found in the Investigator's Brochure.

Procedural risks

Cardiac catheterization is a safe procedure when performed by an experienced medical team. However, there may be some possible risks such as bleeding, infection, and blood clots. A heart attack or a stroke can happen in very rare situations. Right heart catheterization (RHC) is regularly employed to monitor the course of PAH. RHC may be performed without radiation but for optimal placement of the catheter, the investigator can employ x-ray to double-check the positioning of the catheter when measurements are made. RHC does not employ contrast media. RHC is required to calculate PVR. PVR was the primary efficacy assessment of the

parent study, CLTP001A12201, and is performed at Week 26 in the current study, which allows the assessment of the 1-year effect of LTP001 of those participants who received LTP001 already in the parent study, and the 6-month effect on PVR of those who received placebo in the parent study. This data is considered very important to assess the long-term effect of LTP001 on PVR in patients with PAH.

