4.1 Overall design

Please refer to [Section 1.2 Schema](#) for study design figure.

This is a non-randomized, open-label extension study over 52 weeks with LTP001 without a control treatment arm. Participants will be presented the opportunity to consider the extension study at the End of Treatment (EOT) visit (Week 25) of the parent study CLTP001A12201. The investigator will assess if the participant will continue by verifying that the participant has completed the parent study as planned. Moreover, at the EOT the investigator will determine the eligibility for the extension study (i.e. that none of the treatment discontinuation criteria were met and that the assessments at the EOT of the parent efficacy study were completed according to the parent protocol). The patient may directly continue into the extension study. If the patient does not directly continue in the extension study, the time between the end of treatment assessments in the parent study and the enrollment in the extension study i.e. during the transition period should be kept to a minimum (it should not exceed 14 days).

Participants who are eligible and want to participate in the extension study will need to have signed an informed consent in order to receive the extension study treatment. In case of a direct transition into the extension study after the end of treatment visit in the parent study, as not all assessment results will be available (e.g. the central lab assessments) at the same day the investigator will re-assess/reconfirm the eligibility as soon as outstanding results are received.

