Women are considered post-menopausal if they have had 12 months of natural (spontaneous) amenorrhea with an appropriate clinical profile (e.g. age appropriate history of vasomotor symptoms). Women are considered not of child-bearing potential if they are post-menopausal or have had surgical bilateral oophorectomy (with or without hysterectomy) or total hysterectomy at least six weeks ago. In the case of oophorectomy alone, only when the reproductive status of the woman has been confirmed by follow up hormone level assessment is she considered not of child bearing potential.

5. Pregnant or nursing (lactating) women, where pregnancy is defined as the state of a female after conception and until the termination of gestation, confirmed by a positive hCG laboratory test.
6. Acute or chronic impairment (other than dyspnea), which would limit the ability to comply with study requirements, including interference with physical activity or execution of study procedures such as 6MWT (e.g., angina pectoris, claudication, musculoskeletal disorder, need for walking aids).
7. Permanent discontinuation of Novartis drug in the core efficacy study due to toxicity or disease progression despite active treatment, non-compliance to study procedures, withdrawal of consent or any other reason.

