9.4 Secondary endpoint(s)/estimand(s) analysis

9.4.1 Efficacy and/or pharmacodynamic endpoint(s)

Change from baseline for efficacy endpoints including the right heart catheterization (RHC) parameters, 6-Minute Walk Distance (6MWD), and N-terminal fragment of the prohormone B-type natriuretic peptide (NT-proBNP) will be descriptively summarized by visit/time for treatment group (treatment received in the parent study), and overall. The baseline measurement for the extension will be the baseline measurement taken during the parent study CLTP001A12201. Graphs (e.g., spaghetti plot) will be provided to show individual time courses of parameters for the extension study together with the parent study.

Additionally, changes from baseline for efficacy endpoints will be descriptively summarized by visit/time for treatment group (treatment received in the parent study), and overall using a different baseline strategy: participants receiving LTP001 in the parent study will use the baseline of parent study as the baseline; participants switching from placebo in parent study to LTP001 in extension study will use the baseline of extension study as the baseline.

Time to clinical worsening will be analyzed using survival analysis (i.e., Kaplan-Meier) and the corresponding 80% confidence interval will be computed using the appropriate method.

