2.5.1 Primary endpoint(s)

Safety assessment will include AEs, SAEs, vital signs, ECGs, and safety laboratory measurements.

Adverse events (AEs)

All Adverse events in the extension study will be summarized and listed. Also, all study emergent AEs in both the parent study and extension study will be summarized.

Consistent with the parent study CLTP001A12201 definitions, AEs starting after the first dose of study medication or events present prior to start of treatment but increased in severity based on preferred term will be classified as a treatment emergent AE. The definition of the on treatment period is defined in [Section 2.1.1](#). The following treatment emergent adverse events summaries will be produced:

- by primary system organ class and preferred term
- by primary system organ class, preferred term and maximum severity
- by Standardized MedDRA Query (SMQ) and preferred term.

The number and percentage of participants with adverse events will be summarized.

Separate summaries will be provided for study medication related adverse events, serious adverse events, other significant adverse events leading to discontinuation. In case of sparse events in any of these categories occur, only a listing will be provided if deemed adequate.

The number and percentage of deaths, including on-treatment and post-treatment deaths, will be summarized and listed.

Adverse events of special interest/grouping of AEs is not defined in this study.

Vital signs

Vital signs will include the collection of otic or oral body temperature (recorded in °C), blood pressure (BP) and pulse measurements.

All vital signs data will be listed by participant, and visit/time and if ranges are available, abnormalities will be flagged. Summary statistics (including N, mean, SD, minimum, median, maximum) of vital signs and changes from baseline will be provided by visit/time. Graphical presentations (e.g., boxplots) of vital signs will be provided by visit/time.

Electrocardiogram (ECG)

All ECG data, including PR, QRS, QT, QTcF and RR, will be listed by participant and visit/time, and abnormalities will be flagged. Summary statistics and graphical presentations (e.g. boxplots) will be provided by visit/time.

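### No split by parent treatment is specified for the extension AE tables, so the natural single LTP001 column would mix new starters with participants already about 25 weeks into LTP001

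*Protocol*

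**What the plan says.** The primary objective is long-term safety. Protocol 9.3.1 states: "Study emergent AEs in the extension study will be summarized and listed". SAP 2.5.1 states: "All Adverse events in the extension study will be summarized and listed". Both give counts and percentages of participants by organ class and preferred term, by maximum severity and by SMQ. The SAP adds summaries of related AEs, SAEs and AEs leading to discontinuation. No AE sentence in either document names a grouping by parent treatment.

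The more general rules do not supply one:

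- Protocol 9.1, repeated in SAP 2.2: "For all analysis sets, participants will be analyzed according to the study treatment(s) received". Protocol 4.4 plans LTP001 for everyone in the extension.
- SAP 2.2.1 lists no subgroup of interest.
- SAP 2.1 promises a treatment-group difference, but only within change-from-baseline values. That can reach vital signs, ECGs and laboratory data, not AE counts.
- Duration of exposure (Protocol 9.2.3, SAP 2.4.1) is summarised without a split.

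Efficacy is handled differently. Protocol 9.4.1 summarises it "for treatment group (treatment received in the parent study), and overall", and SAP 2.6.1.1 uses parent-study groups for each efficacy endpoint.

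Both documents also plan a summary of AEs from the parent and extension studies together. Its grouping is not stated either.

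**The concern.** The extension enrols two populations with different LTP001 histories, and the protocol recognises this. Section 2.3 justifies the Week 26 catheterisation as giving a one-year effect in those already on LTP001 and "the 6-month effect on PVR of those who received placebo in the parent study". The same distinction is not carried into the AE tables.

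The groups also differ by selection. Exclusion criterion 7 removes participants with "Permanent discontinuation of Novartis drug in the core efficacy study due to toxicity or disease progression despite active treatment", among other reasons. It applies to both parent arms, but only among continuers does it remove people who could not tolerate LTP001. Switchers have not yet been tested in that way.

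In one pooled column, AEs that arise soon after starting LTP001 come almost only from switchers, and AEs that arise after a year of LTP001 can come only from continuers. Both are divided by everyone. The percentage then describes neither the risk on starting LTP001 nor the risk after long exposure, and the second is what a long-term safety objective most needs.

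**Working it through.** The documents give no sample-size calculation, allocation ratio or AE precision target, so there is no planned figure to reproduce. What follows is illustrative.

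**Inputs**

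- Extension size: "approximately 40 participants are planned to complete the parent study CLTP001A12201 and meet the study entry criteria" (Protocol 1.1), so N = 40.
- Prior exposure of continuers: rollover is "at the End of Treatment (EOT) visit (Week 25) of the parent study CLTP001A12201" (Protocol 4.1), so about 24-25 weeks; 25 is used below. Switchers: 0.
- Extension treatment: up to 52 weeks (Protocol 1.1), taken as completed by all.
- Continuers : switchers: not stated. Assumed 20:20 (1:1) and 27:13 (about 2:1).

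**Step 1. Exposure covered.** Switchers contribute LTP001 weeks 0 to 52. Continuers contribute weeks 25 to 25 + 52 = 77. Total person-time is 40 × 52 = 2080 weeks.

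| Cumulative LTP001 weeks | Who contributes | 20:20 | 27:13 |
|---|---|---|---|
| 0-25 | switchers only | 20 × 25 = 500 (24%) | 13 × 25 = 325 (16%) |
| 25-52 | both | 40 × 27 = 1080 (52%) | 40 × 27 = 1080 (52%) |
| 52-77 | continuers only | 20 × 25 = 500 (24%) | 27 × 25 = 675 (32%) |

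**Step 2. Dilution of early-onset AEs.** Let s be the switcher share, p the incidence in switchers and c the incidence in continuers. The pooled percentage is s·p + (1 − s)·c. When c = 0 this is s·p, so the dilution factor is s: 20/40 = 0.50 at 20:20 and 13/40 = 0.325 at 27:13. For an illustrative p = 20%:

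- 20:20: 10% if c = 0; 0.5 × 20 + 0.5 × 5 = 12.5% if c = 5%.
- 27:13: 0.325 × 20 = 6.5% if c = 0; 6.5 + 0.675 × 5 = 9.9% if c = 5%.

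Outside the assumed range, s is 0.25 at 30:10 and 0.675 at 13:27. The dilution changes in size but is present at every split.

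**Step 3. Events possible only after 52 weeks of LTP001.** Only continuers can reach this window, after about 52 − 25 = 27 weeks in the extension. The one-sided 95% upper limit for zero events in n people is 1 − 0.05^(1/n):

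- n = 40: 7.2%
- n = 27: 10.5%
- n = 20: 13.9%

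If the true late risk were 5%, the chance of at least one event, 1 − 0.95^n, would be 87.1% with 40 at risk, 75.0% with 27 and 64.2% with 20. Continuers who leave before week 52 of LTP001 lower n further.

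**The case against.** **The single column is nowhere prescribed.** This is correct. It is inferred from silence plus the treatment-received rule. SAP 2.1.1 refers to study treatment as LTP001 or placebo when defining study day, and Protocol 9.4.1 defines treatment group by parent treatment, so two AE columns could be produced without contradicting the plan. SAP 2.2.1 does not settle it, since efficacy is split by parent arm under the same SAP. A reader might infer that the documents require pooling. They do not. They leave the grouping open, and pooling is the most natural outcome.

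**The combined parent-plus-extension summary may recover early AEs in continuers.** In part, yes: it brings in their first 25 weeks or so on LTP001. But its grouping is also unstated, so it is not an assured remedy.

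**No AE interval is planned.** Correct. Protocol 9.3.2 and SAP 2.5.2 limit the analysis to counts and summary statistics. A reader might infer that the plan will report an over-precise bound on late risk. It will not. The limits in the working show only what a zero count can support.

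**The pooled denominator is often right.** Also correct. Between weeks 25 and 52 of LTP001 both groups contribute, and that window holds about half the extension person-time. Neither document defines long-term as more than 52 weeks.

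**AEs are only one part of the primary endpoint.** Correct. The change-from-baseline rule in SAP 2.1 may already give a group comparison for vital signs, ECGs and laboratory data.

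**Conclusion.** The point stands for extension AE counts. The plan specifies no split by parent treatment, and followed as written it most naturally gives one LTP001 column that combines weeks 0-52 with about weeks 25-77.

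Dilution of early-onset AEs by the switcher share is the firmer part. It follows under any allocation and leaves about one half of the switcher incidence at 1:1 and one third at 2:1 when continuers have none of the event.

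The late-event point is narrower. Beyond 52 weeks of cumulative LTP001, those who can be at risk number about 20-27 rather than about 40.

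These sizes rest on about 40 entrants, an assumed allocation, complete 52-week follow-up and illustrative event rates. The documents do not support reading this as a flaw in the whole primary endpoint, or as a wrong denominator throughout the extension. The change should be made because efficacy already has the split and the primary safety tables do not.

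**What to change.** In Protocol 9.3.1 and SAP 2.5.1, state that the extension AE, SAE, related-AE and discontinuation tables are shown in three columns: LTP001-to-LTP001, placebo-to-LTP001, and overall. Split duration of exposure (Protocol 9.2.3, SAP 2.4.1) in the same way. State the grouping of the combined parent-plus-extension AE summary too.

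If a table by time since first LTP001 dose is added, build it from the combined parent and extension data. Count only time on LTP001, include LTP001 exposure and AEs from the parent study, and use the number at risk or person-time in each interval as the denominator. An extension-only version with a first interval of, say, 0-26 weeks would count continuers who have only one or two weeks left in it, and so bring the dilution back.

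The cost is SAP wording and extra columns. No new data are needed, and the efficacy tables already require parent treatment at analysis. The downside is small cell counts per column, which is acceptable in descriptive tables that keep the overall column. The split does not remove the selection of continuers through exclusion criterion 7, so a footnote should say so.
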